### **5.8.2 Vital signs and physical examination**

Vital signs will be summarized as described in the CTP Section 14.3.13.2 Physical examination will be tabulated in a shift table and in a listing.

### **5.8.3 Clinical laboratory evaluation**

Laboratory parameters will be presented by subgroupings of hematology, chemistry, urinalysis and serology parameters.

For the chemistry parameters and the hematology parameters the absolute values and the changes from baseline will be presented by visit for each treatment group.

Shift tables will be produced for chemistry and hematology parameters showing the thresholds at baseline against those at end of treatment (Week 16), as specified in the ADRG.

Selected chemistry and hematology parameters will be presented by thresholds at end of treatment and at max post-baseline according to the thresholds specified in the ADRG. For each threshold level the number and percentage of subjects with at least one value within the threshold will be summarized by treatment group with denominator being all subjects in the SAF. All post-baseline measurements (including samples from unscheduled visits) are considered in the max post-baseline thresholds tables.

All laboratory results (including serology and urinalysis) will be presented in the listings.

### **5.8.4 Local laboratory evaluation**

Local laboratory results including urine dipsticks and urine pregnancy tests will be listed. Furthermore, urine dipsticks results will be presented in a shift table.

### **5.8.5 Electrocardiography**

The investigator evaluation of ECG will be tabulated using a shift table from baseline to end of treatment, by treatment group. ECG measurements will also be presented in a listing.

### **5.8.6 Assessment of local tolerability**

Subject assessment of local tolerability will be summarized in a table by week and treatment group. Subject assessment of local tolerability will also be presented in a listing.

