10. CHE subtype(s) will be classified according to local standard clinical practice (see Panel 9). Patch testing is recommended to be performed in accordance with the guideline (1) and if this is considered standard clinical practice at the trial site. For subjects who have had a patch test done within 3 years prior to screening, the results of the most recent patch test will be recorded in the eCRF. For subjects who have not had a patch test within 3 years prior to screening, a patch test will be done. Final reading of the patch test should preferably be performed prior to the baseline visit. If this is not possible, the patch test can be performed later but final reading must be available no later than the Week 8 visit.
11. Treatment compliance will be recorded daily by the subject in the eDiary from Day 1 onwards up to end of treatment/early termination.
12. All returned, opened IMP tubes will be weighed at the trial site.
13. Concomitant medication should be included from 3 months prior to baseline (Day 1) until end of trial (see Section 9.6).
14. Completion of the HESD eDiary will be initiated at least 1 week prior to baseline (Day 1), but preferably already from the date the subjects receive the eDiary. Compliance with the eDiary completion will be reviewed by the trial site staff throughout the trial. Subjects who discontinue IMP but remain in the trial will be asked to continue completing the eDiary until the primary endpoint visit at Week 16. A minimum of 4 HESD scores per week are required throughout the trial to calculate the average. The baseline HESD weekly average will be calculated based on daily assessments during the 7 days immediately preceding the baseline visit (Day -7 to Day -1).
15. Subjects' assessment of local tolerability will be evaluated weekly by the subject in the eDiary from Day 7 onwards up to end of treatment/early termination.
16. Subjects do not have to be fasting for safety laboratory samples.
17. For female subjects of childbearing potential (as defined in the relevant inclusion criterion).
18. The PK blood samples should be taken 2-6 hours post application of IMP.
19. Not applicable at the early termination visit if the subject does not withdraw from the trial, as subjects who discontinue IMP but remain in the trial will continue completing the eDiary until the primary efficacy endpoint visit at Week 16.

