## 11.3 eDiary assessments

At the screening visit, the subjects will receive an eDiary device and eDiary training. The eDiary will be open for entry from 4 pm until midnight. The subjects must start completing the HESD in the eDiary at least 1 week prior to baseline, but preferably from the date the subjects receive the eDiary. The HESD must be completed in the eDiary every evening until Week 16, regardless of IMP discontinuation. Treatment compliance (daily) and subject assessment of local tolerability (weekly) will be evaluated by the subject in the eDiary from baseline up to end of treatment/early termination. Compliance with the eDiary completion will be reviewed by the trial site staff throughout the trial.

THIS DOCUMENT CONTAINS CONFIDENTIAL INFORMATION AND MUST NOT BE COPIED OR MADE AVAILABLE TO ANY THIRD PARTY WITHOUT THE PRIOR WRITTEN CONSENT OF THE LEO PHARMA GROUP

Handout, training, and return of the eDiary is outlined in the schedule of trial procedures (Section 4). Return of the eDiary is not applicable for subjects who discontinue IMP and attend an early termination visit, but do not withdraw from the trial. These subjects will continue completing the eDiary until the primary endpoint visit at Week 16 and will return the eDiary at that visit.

The following assessments will be completed in the eDiary by the subjects in the listed order:

- Daily: HESD (see Section 11.4.3.2).
- Daily: treatment compliance (see Section 9.8.4).
- Weekly: subject assessment of local tolerability (see Section 11.5.4).

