#### 11.5.4 Local tolerability

Subjects will provide an assessment of local tolerability according to the schedule of trial procedures (Section 4).

The subject will complete a weekly assessment of stinging/burning in connection with the IMP applications in the eDiary from Day 7 onwards. The subject will be asked to retrospectively assess the worst stinging/burning in connection with the IMP application during the last week. In addition, the subjects will be asked by the investigator at the end-of-treatment/early termination visit to assess the local tolerability during the last week (see Section 4). The assessment will be done using the 4-point scale shown in Panel 13.

The subject's assessment of local tolerability may be reported as an AE at the discretion of the investigator, even if the investigator does not suspect a local skin reaction related to application of IMP (reporting of e.g. pain or stinging/burning by the subject).

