## 14.3.5 Estimand strategy

### 14.3.5.1 Overview

The analysis of endpoints related to efficacy and health-related quality of life will be based on the full analysis set.

For the analyses based on the Bayesian approach, only the primary estimand using the composite strategy will be used.

For the analyses based on the Frequentist approach, both the primary estimand (using the composite strategy) and the supplementary estimand (using the treatment policy strategy) will be considered for the primary endpoint while only the primary estimand will be considered for the key secondary endpoints (remaining binary endpoints) and other continuous endpoints.

THIS DOCUMENT CONTAINS CONFIDENTIAL INFORMATION AND MUST NOT BE COPIED OR MADE AVAILABLE TO ANY THIRD PARTY WITHOUT THE PRIOR WRITTEN CONSENT OF THE LEO PHARMA GROUP

The primary estimand will use a composite strategy to handle IEs. With a composite strategy, the occurrence of an IE is a component of the endpoint.

A supplementary estimand will use a treatment policy strategy which attempts to quantify the effect of the randomised treatment, ignoring the occurrence of IEs. Data collected for the endpoint of interest are used regardless of whether an IE occurred.

For the composite and treatment policy estimands, prespecified sensitivity analyses will be conducted to assess the robustness of the results with respect to the handling of missing data. The pre-specified sensitivity analysis will only be performed for the primary endpoint as a low IMP discontinuation rate is anticipated in the relatively small sample size (69 subjects on delgocitinib cream vs. 23 subjects on cream vehicle) and the expected low amount of the missing data. These sensitivity analyses will only be performed for the analyses based on the Frequentist approach when mentioned.

In addition, sensitivity analyses of the influence of weight on the non-informative part of the prior will be made for the Bayesian approach, see Section [14.3.17](#).

The following IEs are considered to affect the interpretation of the estimated treatment effects:

- **Initiation of rescue treatment:** This IE occurs when a subject initiates rescue treatment. This IE can occur at the discretion of the investigator. If rescue treatment is initiated, the subject must stop treatment with IMP immediately and will not be allowed to restart treatment with IMP (refer to Section [9.5](#) for details).

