## **5 Statistical analysis**

### **5.1 General principles**

All frequentist significance tests will be one-sided using the 2.5% significance level. Operationally, the one-sided (superiority) hypotheses will be evaluated by deriving the two-sided p value; the null hypothesis will be rejected if the p value is smaller than 5% and if the point estimate is in favor of the alternative hypothesis.

All confidence intervals will be presented with 95% degree of confidence, unless otherwise specified.

An observed-cases approach will be used for tabulations of data by visit (that is, involving only those subjects who attended each specific visit).

Categorical data will be summarised using the number and percentage of subjects in each category and treatment group. Continuous data will be summarised using the mean, median, SD, 1st quartile, 3rd quartile, minimum, and maximum values.

Baseline measurements will be defined as the latest available observation at or prior to the date of randomization. Subjects without a baseline measurement for a given efficacy score will be excluded from the corresponding analysis.

In case of randomization in wrong stratum with respect to baseline IGA-CHE score, the statistical analyses will use the baseline IGA-CHE score confirmed by the investigator in the eCRF. This is due to the fact that the disease severity according to baseline IGA-CHE score is considered to be a strong prognostic factor for the treatment effect.

Simulation seed used for MI will be 1331426 for both types of imputation (MI based on MAR and MI based on Bernoulli distribution).

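### Stinging/burning is tabulated only by week, so later percentages can fall if affected subjects stop IMP; add a table of worst grade per subject over the safety set

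*SAP*

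**What the plan says.** **Collection.** Footnote 15 of the protocol's schedule (Panel 2) has local tolerability "evaluated weekly by the subject in the eDiary from Day 7 onwards up to end of treatment/early termination". Each entry asks the subject to "retrospectively assess the worst stinging/burning in connection with the IMP application during the last week" (Protocol 11.5.4). A further rating is taken when treatment ends: "the subjects will be asked by the investigator at the end-of-treatment/early termination visit to assess the local tolerability during the last week". In Panel 2 the early termination visit carries no week or day number. The symptom diary is handled differently: "The HESD must be completed in the eDiary every evening until Week 16, regardless of IMP discontinuation" (Protocol 11.3). Tolerability has no such continuation.

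**Analysis.** SAP 5.8.6 consists of two statements: "Subject assessment of local tolerability will be summarized in a table by week and treatment group", and "Subject assessment of local tolerability will also be presented in a listing". It gives no denominator, no summary of the worst grade per subject, and no row for the early termination rating. The nearest general rule is in SAP 5.1: "An observed-cases approach will be used for tabulations of data by visit". That sentence is written for visits, not diary weeks.

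**Context.** Protocol 5.5 names burning and stinging among the local reactions that may occur with this type of product. Footnote 1 to Protocol Panel 4 lists local tolerability among the assessments evaluated alongside the secondary safety endpoint. Protocol 14.3.5.1 expects few subjects to stop IMP but gives no figure. Its planned arm sizes are "69 subjects on delgocitinib cream vs. 23 subjects on cream vehicle".

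**The concern.** A reader of the tolerability results will want to know what share of exposed adolescents had stinging or burning, and how bad it was at worst. A by-week table does not answer that. Each weekly percentage describes the subjects who still contribute a rating in that week. Someone who stops IMP leaves numerator and denominator together, so a falling percentage may mean that the skin settled, that affected subjects left, or both. The table alone cannot separate these.

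A second gap concerns very early stops. The first diary rating falls on Day 7, so a subject who stops before then has only the rating taken at the early termination visit. The SAP gives that rating no place in a table arranged by week, although it comes from the subjects for whom tolerability may matter most.

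At stake is the descriptive account of local tolerability. No test or confirmatory conclusion depends on it.

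**Working it through.** The documents state no figure for local tolerability, so there is none to reproduce.

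**Inputs**
- Arm sizes: N = 69 and N = 23 (Protocol 14.3.5.1), taken here as all exposed.
- Number with persistent stinging, s: not in the documents. Assumed to be about 10% or 20% of the delgocitinib arm (7 or 14) and 2 in the vehicle arm.
- Number of those who stop IMP, k: not in the documents. Assumed to lie between 0 and 5.
- Stinging in each affected subject is held constant, all diaries are completed, and nobody else stops.

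**Formulas**
- Early weekly share: s/N.
- Later weekly share among those still rated: (s − k)/(N − k).
- Share ever affected, over all exposed subjects: s/N whatever k is, provided each affected subject has at least one rating.

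**Results**

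| Arm | s | Early week | k | Later week | Worst grade over all exposed |
|---|---|---|---|---|---|
| Delgocitinib | 7 | 7/69 = 10.1% | 0 | 7/69 = 10.1% | 10.1% |
| Delgocitinib | 7 | 10.1% | 1 | 6/68 = 8.8% | 10.1% |
| Delgocitinib | 7 | 10.1% | 3 | 4/66 = 6.1% | 10.1% |
| Delgocitinib | 7 | 10.1% | 5 | 2/64 = 3.1% | 10.1% |
| Delgocitinib | 14 | 14/69 = 20.3% | 3 | 11/66 = 16.7% | 20.3% |
| Delgocitinib | 14 | 20.3% | 5 | 9/64 = 14.1% | 20.3% |
| Vehicle | 2 | 2/23 = 8.7% | 1 | 1/22 = 4.5% | 8.7% |
| Vehicle | 2 | 8.7% | 2 | 0/21 = 0% | 8.7% |

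**When the fall occurs.** Suppose m subjects stop in total and k of them have stinging. The later share is (s − k)/(N − m). This is below s/N exactly when k/m exceeds s/N, that is, when stinging is over-represented among those who stop. If stopping is unrelated to stinging, the expected share does not change. If subjects without stinging stop more often, it rises. The weekly percentage can therefore mislead in either direction, and with 23 vehicle subjects one departure is enough to move it visibly.

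**Stops before Day 7.** These subjects have no diary entry, so they add nothing to any weekly diary row. They enter a worst-grade table only if it uses the early termination rating.

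**The case against.** There is a good case that little is wrong here.

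- A reader might infer that stinging must appear to fade with time on drug, as a built-in consequence of the design. The documents do not support that. A fade needs stops related to stinging, no such rate is given, and few discontinuations are expected. An illustration in which all 7 affected subjects stop, leaving 0 of 62, is the extreme case.
- A subject with severe stinging who reaches Day 7 and completes the diary is counted in that week's row, because the item asks for the worst of the past week. Only stops before Day 7 leave no diary entry.
- A reader might also infer that early severe cases vanish from the report. They do not. All ratings are listed (SAP 5.8.6). Adverse events leading to discontinuation of IMP are summarised by arm over the safety set and listed (SAP 5.8.1). Reasons for stopping are shown by last visit attended (Protocol 14.3.1), intercurrent events by visit interval (SAP 5.3), and time to discontinuation by Kaplan-Meier plot (SAP 7.3.2).
- The SAP is silent on where the early termination rating goes and on whether diary and investigator-asked ratings share a row. Silence does not show that the rating is left out or that the two are merged. SAP Section 1 refers data handling to the analysis data reviewer's guide and define.xml, which are not available here. Applying the observed-cases rule to diary weeks is likewise an inference.
- Ending collection with IMP is natural for an item about stinging on application.

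All of this stands, and it limits the point to the summary table. It does not remove it. A listing is not a proportion by arm. Stinging becomes an adverse event only if the investigator chooses to report it (Protocol 11.5.4). The disposition summaries show how many subjects stopped, but they do not cross-classify them by stinging grade.

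**Conclusion.** The point holds as a minor reporting gap. The only planned tabulation of the stinging/burning score is by week and arm, and the early termination rating has no stated place in it. No planned table gives the proportion of exposed subjects by worst grade. A weekly trend therefore cannot be read on its own as tolerance developing.

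The size rests entirely on assumed inputs. With 7 of 69 delgocitinib subjects affected throughout, the later weekly figure would be 8.8% to 3.1% instead of 10.1% if 1 to 5 of them stop, and there is no distortion if none stop. The documents do not support saying that a fade will occur, or that tolerability cases are lost from the report. The primary and key secondary analyses are unaffected.

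**What to change.** In SAP 5.8.6:

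1. Add a table of the worst post-baseline stinging/burning grade per subject, by treatment group, using the weekly diary entries and the end-of-treatment/early termination rating, with the safety analysis set as denominator. Include a row for subjects with no rating at all, so that they are not silently counted as free of stinging.
2. Keep the by-week table as descriptive. For each week show the number assessed and the number still on IMP.
3. State where the early termination rating is presented.

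The SAP already takes this approach for laboratory thresholds: SAP 5.8.3 tabulates the maximum post-baseline value over the safety analysis set and includes unscheduled samples. The cost is one extra table from data already collected, with no change to procedures or visits. The reported tolerability may look slightly less favourable.

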### **5.8.7 New CHE lesions**

New CHE lesions after baseline will be listed for randomised subjects.

## **5.9 Subgroup analyses**

No subgroup analysis planned.

## **5.10 Interim analysis**

No interim analysis planned.

# **6 Changes to analyses described in the protocol**

In the analysis with the historical data, it is described that the associated 95% confidence interval will be based on the standardised estimator presented in Ge M et al. (2).

This has been changed so the associated 95% confidence interval will be estimated based on the delta method instead.

## 7 Supporting documentation

### 7.1 Appendix 1: Patient reported outcome scoring algorithms

The PROs scoring algorithms are specified in [Panel 24](#).

#### Panel 24: Patient reported outcome scoring algorithms

cDLQI	Scored according to: https://www.cardiff.ac.uk/medicine/resources/quality-of-life-questionnaires/childrens-dermatology-life-quality-index .
HESD	
HESD includes 6 items (itch, pain, cracking, redness, dryness, and flaking). HESD score is derived as an average of the 6 items. The daily HESD score may only be calculated if at least 3 items are available per day. The weekly HESD score is then calculated as the average of the daily HESD scores for the week, if at least 4 days are available.
 
For the individual HESD items an average per week can be calculated if data from at least 4 days is available.
 
The HESD weekly average scores at baseline and Week 16 will be calculated from daily assessments of HESD during the 7 days immediately preceding the baseline visit (Day -7 to Day -1) and the Week 16 visit (Day of Week 16 visit -7 to Day of Week 16 visit -1). For the HESD weekly average scores between baseline and Week 16 it will be the nominal weekly averages, meaning that the average isn't related to the actual visit. For further details on the derivation of the HESD weekly average scores refer to the ADRG.(4)

### 7.2 Appendix 2: SAS- and R-code

#### 7.2.1 SAS code for multiple imputation

```
proc mi data = inddata nimpute = 100 out = uddata seed = 1331426;
  where trt01pn=treatment;
  class w0 w30 w40 w50 w60 w70;
  var w0 w30 w40 w50 w60 w70;
  fcs logistic(W30 = W0 W40 W50 / likelihood=augment);
  fcs logistic(W40 = W0 W30 W50 W60 / likelihood=augment);
  fcs logistic(W50 = W0 W30 W40 W60 W70 / likelihood=augment);
  fcs logistic(W60 = W0 W40 W50 W70 / likelihood=augment);
  fcs logistic(W70 = W0 W50 w60 / likelihood=augment);
run;
```

THIS DOCUMENT CONTAINS CONFIDENTIAL INFORMATION AND MUST NOT BE COPIED OR MADE AVAILABLE TO ANY THIRD PARTY WITHOUT THE PRIOR WRITTEN CONSENT OF THE LEO PHARMA GROUP

where IGA-CHE score at baseline (Week 0) is contained in the variable IGABL, the score of the variable of interest at Week 1 is contained in the variable w1, and similarly for other visits.

### 7.2.2 R code for Bayesian analyses

Calculation of Beta-mix components for prior distribution done before DBL and unblinding of data:

```
seed.Veh<-1331426
seed.del<-1331426
weight.value <- 0.2
tau.priorvalue <- 0.5

map_mcmc_veh <- gMAP(cbind(r, n-r) ~ 1 | study, data=xxx,
tau.dist="HalfNormal",
                    tau.prior=tau.priorvalue, beta.prior=100,
family=binomial, iter=50000, warmup=5000,
                    thin=5, init = 1, chains=6,cores=1L)
```

Conversion of the MAP prior to a parametric representation with the automixfit function:

```
map <- automixfit(map_mcmc_veh, k=10)
```

Robustification of parametric representation of the prior:

```
map_robust <- robustify(map, weight=weight.value,
mean=1/2,tau.prior=tau.priorvalue)
```

The parameter settings and number of iterations mentioned above will not be changed after DBL. The code mentioned below will be run on unblinded data. Here, the number of iterations may be increased if results are not clearly interpretable.

Calculation of the posterior distribution

```
post <- postmix(prior, r = number of responders, n = number of randomised)
```

Calculation of probability that the difference is smaller than 0

```
prob_smaller_iga <- pmixdiff(post_trt1, post_trt2, 0, lower.tail=FALSE)
prob_smaller_iga > 0.975
```

Sampling of 1.000.000 differences between posteriors

```
rM_iga <- rmixdiff(post_trt1, post_trt2, n=1E6)
rM_mean_iga<- mean(rM_iga)
```

THIS DOCUMENT CONTAINS CONFIDENTIAL INFORMATION AND MUST NOT BE COPIED OR MADE AVAILABLE TO ANY THIRD PARTY WITHOUT THE PRIOR WRITTEN CONSENT OF THE LEO PHARMA GROUP

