#### 14.3.17 Description of the Bayesian analyses and design characteristics

The design characteristics is based on 92 randomised subjects (69 in the delgocitinib cream 20 mg/g group and 23 in the cream vehicle group).

For each endpoint, the choice of the between-trial heterogeneity parameter ( $\tau$ ) and the weight on the non-informative part of the prior is described. In addition, the degree of borrowing is described by the ESS and finally, the influence of the type I error and power investigated.

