##### 14.3.17.1 Overview of the Bayesian procedure

The R Bayesian evidence synthesis tools (R package RBesT) ([42](#), [43](#)) will be applied. The steps in the analysis are listed below.

1. **Create informative prior:** The MAP approach, using a hierarchical model for between-study heterogeneity, will be applied to derive an informative prior from historical data (the pivotal trials LP0133-1401 and LP0133-1402 and where applicable, phase 2b trial LP0133-1273) for the cream vehicle as well as for the delgocitinib cream 20 mg/g treatment group.
2. **Parametric mixture densities:** The expectation maximization algorithm is used to approximate parametric mixture densities to the MCMC samples representing the MAP prior. The mixture providing the best Akaike information criterion value is selected.
3. **Robustification of the informative prior:** The informative mixture prior is robustified by adding a non-informative component which protects against type I error inflation in presence of prior-data conflict, i.e. if the adolescent trial data strongly deviate from the historical information. The weight put on the non-informative part is prespecified for each endpoint. The influence of the weight on the ESS, the type I error and power for the trial will be described.
4. **Posterior distribution:** Once the data from the adolescent trial is unblinded, the posterior distributions for the proportion of responders for each treatment group, given the robust mixture priors, are calculated.
5. **Treatment effect evaluation:** Conclusion on treatment effect will be based on the calculated difference in the posterior distributions.

THIS DOCUMENT CONTAINS CONFIDENTIAL INFORMATION AND MUST NOT BE COPIED OR MADE AVAILABLE TO ANY THIRD PARTY WITHOUT THE PRIOR WRITTEN CONSENT OF THE LEO PHARMA GROUP

- a. Statistically significant treatment effect is concluded if the probability that the difference (delgocitinib cream 20 mg/g minus cream vehicle) is larger than zero, is larger than 0.975.
- b. 95% credibility interval is generated as the 2.5% and 97.5% quantiles of the difference in posterior distributions.
- c. Median and mean are calculated from the difference in posterior distributions.

6. **Sensitivity/tipping point analyses (given the unblinded results):** Will be done to evaluate the influence of the prespecified selected  $\tau$  and the prespecified selected weight parameter for the non-informative part of the prior.

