#### 14.3.17.2 Evaluation of design characteristics (type I error, power and bias) for the Bayesian analysis of the primary endpoint

The between-trial heterogeneity for the primary endpoint IGA-CHE TS is set to  $\tau = 0.5$ , the weight on the non-informative part of the prior is set to 0.2 (20%).

This ensures a type I error <5% for efficacy rates <10% (average observed efficacy rates for cream vehicle was 8.4% in the adult trials LP0133-1401 and LP0133-1402) and a high power (>75%) for efficacy levels above observed efficacy levels (average difference in adult trials is 15.9%).

In the following sections, the selection of the parameters for the primary endpoint IGA-CHE TS are justified and discussed.

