#### Panel 22: Summary of MAP for cream vehicle

	Mean	SD	Median	2.5% quantile	97.5% quantile
Between-trial heterogeneity of $\tau$ prediction stratum	0.33	0.26	0.27	0.01	0.97
MAP Prior MCMC sample	0.097	0.058	0.086	0.031	0.245

[figure not shown]
**Abbreviations:** MAP: meta-analytic-predictive, MCMC: Markov chain Monte Carlo, SD = standard deviation.

A forest plot of trials LP0133-1401 and LP0133-1402 and the MAP is shown in [Panel 23](#).

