## 2 Testing strategy

### 2.1 Testing hierarchy and statistical hypothesis

The Bayesian analyses of the primary estimand for the primary and key secondary endpoints are considered the confirmatory evidence for the trial.

The treatment effect (defined as proportion of responders for delgocitinib cream 20 mg/g minus the proportion of responders for cream vehicle) for all the binary confirmatory endpoints will be evaluated based on the calculated difference of posterior distributions for delgocitinib cream 20 mg/g and cream vehicle.

[figure not shown]
Delgocitinib cream 20 mg/g is considered superior to cream vehicle if the 2.5% percentile of the posterior distribution of the treatment difference is  $\geq 0$ .

Hierarchical evaluation, which is applied for the Bayesian analyses, will be used to control the overall type I error at a nominal one sided 2.5% level. This is built on the principle that the IGA-CHE TS superiority at Week 16 will have to be established before sequential testing for additional benefits (key secondary endpoints) related to efficacy.

If superiority is claimed for the primary endpoint, then evaluation of the next endpoints will be done in a fixed sequential order as specified in [Panel 4](#). This process will be repeated until no further tests are significant.

Only analyses based on the Bayesian approach will be part of the testing hierarchy.

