**Panel 10: Beta mix components for the prior distribution for IGA-CHE vehicle responders from LP0133-1401 and LP0133-1402**

	Component 1	Component 2	Component 3	Component 4	Robust
W	0.42	0.28	0.06	0.04	0.20
A	16.36	3.44	5.86	1.16	1.00
B	180.23	39.78	35.60	5.07	1.00

**Note:** Not rounded data can be found in /leo/clinical/lp0133/1426/stat/sap/rob\_viga.xpt.

**Panel 11: Beta mix components for the prior distribution for IGA-CHE delgocitinib 20 mg/g responders from LP0133-1401 and LP0133-1402**

	Component 1	Component 2	Component 3	Component 4	Robust
W	0.38	0.16	0.13	0.12	0.20
A	21.30	6.35	1.55	14.15	1.00
B	66.59	30.83	3.26	27.17	1.00

**Note:** Not rounded data can be found in /leo/clinical/lp0133/1426/stat/sap/rob\_diga.xpt.

THIS DOCUMENT CONTAINS CONFIDENTIAL INFORMATION AND MUST NOT BE COPIED OR MADE AVAILABLE TO ANY THIRD PARTY WITHOUT THE PRIOR WRITTEN CONSENT OF THE LEO PHARMA GROUP

Once the trial is unblinded the posterior distributions for the proportion of responders for vehicle and delgocitinib 20 mg/g for IGA-CHE given the robust mixture priors can be calculated with the 'postmix' function in the statistical package 'RBesT'.

The conclusion on treatment effect will be based on the calculated difference (based on 1.000.000 samples) in the posterior distributions. A statistically significant treatment effect is concluded if the probability that the difference (delgocitinib cream 20 mg/g minus cream vehicle) is larger than zero, is larger than 0.975. That is if  $P(\text{delgocitinib cream 20 mg/g} - \text{cream vehicle} > 0) > 0.975$ . The 95% credibility interval (generated as the 2.5% and 97.5% quantiles of the difference in posterior distributions) will be presented along with the mean and median.

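### The IGA-CHE TS priors fixed in the SAP are not the priors summarised in the protocol; the change is not listed, and it lifts type I error at the adult vehicle rate to 2.8%

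*SAP*

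**What the plan says.** Protocol 14.3.17.2 builds the IGA-CHE TS priors from the two adult phase 3 trials (vehicle 16/162 and 11/159; delgocitinib 64/325 and 91/313), with tau 0.5 and weight 0.2 on the non-informative component. The row "MAP Prior MCMC sample" of Protocol Panel 22 gives the vehicle prior a mean of 0.097, SD 0.058, median 0.086 and 95% range 0.031 to 0.245. Panel 26 gives delgocitinib a mean of 0.26 and a range of 0.09 to 0.55. Panels 25 and 29 print the robustified mixtures with integer beta parameters. No intercept prior is stated. Of the chosen setting, the protocol says "This ensures a type I error <5% for efficacy rates <10" per cent, with power above 75%.

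SAP 5.5.1.7 uses the same counts, tau and weight. SAP Panel 10 ("Beta mix components for the prior distribution for IGA-CHE vehicle responders from LP0133-1401 and LP0133-1402") and Panel 11 print the mixtures to two decimals, and the text declares them fixed. The code in SAP 7.2.2 contains "tau.prior=tau.priorvalue, beta.prior=100". SAP 2.1 says the hierarchy will "control the overall type I error at a nominal one sided 2.5% level". SAP Section 6 records one departure from the protocol, in the analysis that pools historical data: "This has been changed so the associated 95% confidence interval will be estimated based on the delta method instead". SAP Section 3 refers to the protocol for sample size, and the SAP gives no type I error, power or ESS of its own.

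**The concern.** The Bayesian analysis is the trial's only confirmatory evidence, and the vehicle arm has 23 subjects against a stated prior ESS of about 55. The vehicle prior therefore carries much of the decision. If the prior to be used is not the one summarised beside the protocol's error and power claims, those claims need not describe the analysis that will be run.

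SAP 5.5.1.9 varies tau and the robust weight but not the intercept prior, so the planned sensitivity analyses would not reveal this. Protocol 14.3.15 asks for changes to planned analyses to be described and justified.

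**Working it through.** **Inputs.** Counts from Protocol Panel 21 and SAP Panel 9; mixtures from Protocol Panels 25 and 29 and SAP Panels 10 and 11 (weights rescaled to sum to 1, because two panels sum to 1.01 and 0.99 after rounding); sample sizes "69 in the delgocitinib cream 20 mg/g group and 23 in the cream vehicle group"; success if the posterior probability that the difference "is larger than zero, is larger than 0.975".

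**1. Which setting explains the difference?** The model is r_j ~ Bin(n_j, p_j), logit p_j = mu + tau·z_j, with z_j ~ N(0,1), mu ~ N(0, s²) and tau ~ half-normal(0.5). It was refitted by numerical integration, changing only s. The table shows the MAP prior before the robust part is added.

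| Prior | Mean | SD | Median | 95% range |
|---|---|---|---|---|
| Vehicle, Protocol Panel 22 | 0.097 | 0.058 | 0.086 | 0.031-0.245 |
| Vehicle, refit s = 2 | 0.097 | 0.058 | 0.086 | 0.031-0.2445 |
| Vehicle, SAP Panel 10 | 0.0915 | 0.053 | 0.082 | 0.027-0.219 |
| Vehicle, refit s = 100 | 0.091 | 0.052 | 0.082 | 0.027-0.219 |
| Delgocitinib, Protocol Panel 26 | 0.26 | 0.11 | 0.25 | 0.09-0.55 |
| Delgocitinib, refit s = 2 | 0.261 | 0.112 | 0.245 | 0.086-0.553 |
| Delgocitinib, refit s = 100 | 0.256 | 0.110 | 0.241 | 0.078-0.540 |

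With s = 100, the delgocitinib range would print as 0.08-0.54, not 0.09-0.55. Both arms show the same pattern. With s = 100, the refitted vehicle tau (mean 0.326, median 0.263) is close to Panel 22 (0.33, 0.27), so the heterogeneity prior does not appear to have changed.

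**2. Operating characteristics.** Each posterior is a beta mixture with components Beta(a_k + r, b_k + n − r) and weights proportional to w_k·B(a_k + r, b_k + n − r)/B(a_k, b_k). The error at a common rate p is the sum of Bin(r_D; 69, p)·Bin(r_V; 23, p) over all successful outcomes among the 70 × 24.

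The plan's own claim comes first. Printed Panels 25 and 29 give 1.96% at 8.4% and power of 78.8% at 8.4% against 24.3%, which agrees with <5% and >75%.

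| True rate in both arms | Protocol, rebuilt (s = 2) | Protocol, Panels 25/29 | SAP, Panels 10/11 |
|---|---|---|---|
| 8.4% | 1.75% | 1.96% | 2.77% |
| 9.0% | 2.39% | 2.71% | 3.59% |
| 9.9% | 3.53% | 4.10% | 5.00% |
| 10.0% | 3.67% | 4.27% | 5.17% |
| 18.8% | 14.3% | 15.69% | 15.74% |
| Power, 8.4% v 24.3% | 77.5% | 78.8% | 79.0% |

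Rebuilding the SAP prior with s = 100, without mixture rounding, also gives 2.77% at 8.4%.

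**3. Where the change arises.** Two outcomes switch to success:

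- 9/69 against 0/23: posterior probability 0.97499 with printed protocol panels, 0.9775 with SAP panels. Its probability at 8.4% is 0.1329 × 0.0610 = 0.0081, and 1.96% + 0.81% = 2.77%.
- 12/69 against 2/23: 0.97472 with the rebuilt protocol prior, 0.9766 with SAP panels. Its probability is 0.2828 × 0.0073 = 0.0021, and 1.75% + 0.21% = 1.96%.

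**4. Rounding.** Varying the entries of Panels 25 and 29 within their rounding moves the 8.4% figure between 1.75% and 3.72%.

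**The case against.** The strongest reply is that the SAP priors are pre-specified and transparent: code, seed and mixtures are printed, and all are fixed before unblinding. The protocol names no intercept prior, so SD 100 contradicts no protocol text, and 14.3.15 allows changes to be made in the SAP. That stands. What is missing is the declaration and the re-evaluation.

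The effect also turns on one or two outcomes at the 0.975 cut-off, and the rounding range of the printed protocol panels contains 2.77%. This stands as a limit on the protocol-side figure. It does not touch the 2.77%, which the printed SAP panels and the unrounded refit both give.

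A reader might infer several stronger things that the documents do not support:

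- **That the protocol promised 1.8%.** It promises only <5%.
- **That the <5% statement has collapsed.** It holds up to about 9.9% and is exceeded by at most 0.17 points at 10%.
- **That the change causes the large inflation at higher vehicle rates.** Near 19-20% the maximum is about 15.7% under both sets of printed priors.
- **That the change simply favours delgocitinib.** The delgocitinib prior also moved down and partly offsets the vehicle shift: the SAP vehicle prior with the rebuilt protocol delgocitinib prior would give 3.72%.
- **That the SAP vehicle prior carries more information.** Its SD and 95% range are narrower, but its ESS is 57 against 62 for the rounded protocol panel and a stated figure of about 55.
- **That ESS gaps show altered priors for the key secondary endpoints.** Recomputed values (vehicle/delgocitinib) such as 36/72 against a stated 40/90 for HESD, or 31/49 against 35/40 for pain, are compared with approximate readings from plots. No intercept-prior refit was made for those endpoints.

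**Conclusion.** The point holds in limited form. The prior fixed for the primary analysis differs from the one the protocol summarises, the intercept prior accounts for the difference, and the SAP neither lists nor evaluates it. At the adult vehicle rate, type I error is 2.8% rather than about 1.8-2.0%, which puts it above the nominal one-sided 2.5%. The statement of <5% for rates below 10% is marginally untrue just under 10%. The <5% claim at 8.4% and the power claim both survive.

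This rests on three assumptions. The protocol's SD of about 2 is inferred from matching Panels 22 and 26. The full 69 and 23 subjects are analysed. The curves in Protocol Panels 30 and 31, which could not be seen here, were drawn with the summarised priors. If they were drawn with the SAP priors, the mismatch would lie between the protocol's panels rather than in its error figures, but the margin just below 10% would still fail. Nothing in the documents makes SD 2 preferable to SD 100 in itself.

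**What to change.** Before unblinding:

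1. List the intercept-prior setting in SAP Section 6 and justify it.
2. Report type I error, power and ESS recomputed for the fixed SAP priors, for the primary and all key secondary endpoints, over a range of vehicle rates that includes 8.4% to 10%.
3. Restate the <5% below 10% claim and the nominal 2.5% claim to match those results.

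This costs a rerun of existing code and a short SAP revision.

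Alternatively, restore the intercept prior actually used for the protocol panels, which the sponsor can confirm from its own code, and regenerate the SAP panels. Power then falls by up to about 79.0% − 77.5% = 1.5 points and stays above 75%. That choice should rest on consistency with the evaluated design, not on which prior gives the lower error.
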